20.2.1 Withdrawal Procedures

If for any reason a subject is withdrawn or discontinues before completing the final visit, the reason for termination must be recorded in the source documents and reported on the appropriate eCRF. All data gathered on the subject prior to termination will be made available to the Sponsor.

Subjects discontinuing study drug should continue to be fully evaluated per the protocol event schedule, when possible, for safety purposes. However, if the subject discontinues before

Week 6, the second biopsy will not be collected. If a discontinuation occurs on or after Week 6, the second biopsy will be obtained.

21 ADVERSE EVENTS AND SERIOUS ADVERSE EVENTS

21.1 REPORTING RESPONSIBILITY

The Investigator and study staff are responsible for detecting and recording AEs and SAEs, during scheduled safety evaluations and whenever such information is brought to their attention. This section of the protocol provides definitions and detailed procedures to be followed.

During each visit, the Investigator or qualified designee will assess adverse events using an open question that does not to influence the subject's answers, e.g., "have you noticed any change in your health?"

All AEs occurring after signing of the Informed Consent, and at or before the final visit must be reported regardless of suspected relationship to study drug.

All AEs will be evaluated by the Investigator and intensity (severity) and relationships to study drug will be assessed and recorded.

Any AEs already documented at a previous assessment and designated as ongoing, should be reviewed at subsequent visits as necessary. If these have resolved, the resolution date should be documented. Changes in intensity or frequency of AEs should be recorded as separate events (i.e., a new record started).

AEs and SAEs in possible subjects traveling to study sites from countries other than the study site country will be assessed and managed in the same fashion as those appearing in subjects from the study site countries.

21.2 DEFINITION OF AN AE

An AE is any untoward medical occurrence (e.g., sign, symptom, disease, syndrome, intercurrent illness) that occurs in a study subject, following the signing of informed consent, regardless of the suspected cause. Only subjects who have been exposed to study drug (active drug or placebo) can experience treatment emergent AEs. Untoward experiences occurring prior to initiation of first administration of study drug are considered non-treatment emergent AEs.

21.3 SEVERITY

The term of severity is used to describe the intensity of a specific event. The event itself, however, may be of minor medical significance. This is not the same as serious, which is based

on outcome of the event. Seriousness, not intensity, serves as a guide for defining regulatory reporting obligations.

For all AEs, severity will be recorded in the source documents and reported on the appropriate AE eCRF page. There are 3 levels of severity, defined as follows:

Mild: Noticeable, but does not disrupt normal daily activity

Moderate: Sufficient to reduce or disturb normal daily activity

Severe: Incapacitating, significantly interferes with or prevents normal daily activity

21.4 RELATIONSHIP

For all AEs, relationship to study drug will be recorded in the source documents and reported on the appropriate AE eCRF page. The Investigator must judge whether the study drug caused or contributed to the AE, and report it as either:

- Related (definitely, possibly or probably): when there is a reasonable possibility that the study drug caused or contributed to the AE; this conclusion may be supported by the following observations, though these are not required for a determination of related:
 - a) There is a plausible time sequence between onset of the AE and study drug administration;
 - b) There is a plausible biological mechanism through which study drug may have caused or contributed to the AE;

or

- Not related: when it is highly unlikely or impossible that the study drug caused or contributed to the AE; this conclusion may be supported by the following observations, though these are not required for a determination of not related:
 - a) Another cause of the AE is evident and most plausible;
 - b) The temporal sequence is inconsistent between the onset of the AE and study drug administration;
 - c) A causal relationship is considered biologically implausible.

21.5 SERIOUS ADVERSE EVENTS

An AE is serious if:

- it was fatal (i.e., the AE caused or led to death)
- it was life threatening (i.e., the AE placed the subject at immediate risk of death; an AE that hypothetically might have caused death if it were more severe is not an SAE by this criterion)
- it required or prolonged hospitalization (i.e., the AE resulted in a minimum 24 hour hospitalization or prolonged a hospitalization beyond the expected length of stay; hospital admissions for elective medical/surgical procedures, or scheduled treatments are not SAEs by this criterion)
- it resulted in permanent or significant disability/incapacity (i.e., the AE resulted in a substantial disruption of the subject's ability to carry out normal life functions)
- it resulted in a congenital anomaly/birth defect (i.e., an adverse outcome in a child or fetus of a subject exposed to the study drug prior to conception or during pregnancy)
- it required significant medical or surgical intervention to prevent permanent impairment or damage (e.g., hypotension requiring pressers to prevent ischemia, replacement of broken or malfunctioning device).

21.6 SPECIAL REPORTING SITUATIONS

21.6.1 Death

Death is an outcome of an event. The AE that resulted in the death should be recorded and reported as the SAE. If an autopsy is performed, efforts should be made to obtain the results.

21.6.2 Hospitalizations for Surgical or Diagnostic Procedures

The AE leading to the surgical or diagnostic procedure should be recorded and reported as the SAE. The procedure should be reported as an action in response to or treatment for the medical condition.

21.6.3 Pregnancy

Any pregnancy that occurs during the study or within 6 months of the last dose of study drug should be recorded on a Pregnancy Report Form to facilitate outcome follow-up. Pregnancy should be reported whether occurring in a female subject or the partner of a male subject. Spontaneous abortion should be reported as an SAE.

Regardless of subject sex, the Investigator should counsel the subject (and partner, if appropriate) regarding possible effects on the fetus and risks of continuing with the pregnancy. Monitoring should continue until conclusion of the pregnancy.

21.6.4 Inadvertent Exposure or Overdose

Any inadvertent exposure or overdose of study medication should be recorded in the source documents and reported immediately to the Sponsor by phone and email. The exposure and any AEs should be reported of the appropriate eCRF forms.

21.6.5 Suspected Unexpected Serious Adverse Reactions (SUSARs)

SUSARs shall be reported by the Sponsor to the regulatory authorities as applicable and to the relevant ethics committee to fulfill EU regulations (“Detailed guidance on the collection, verification and presentation of adverse reaction reports arising from clinical trials on medicinal products for human use”).

Expedited reporting is required electronically to the regulatory authority and EudraVigilance database as soon as possible, however no later than within seven (7) days of the Sponsor being informed of fatal or life-threatening adverse reaction.

Serious unexpected adverse reactions which are not life-threatening or fatal must be reported to the regulatory authority and EudraVigilance database as soon as possible and in any case within fifteen (15) days of the sponsor first being informed.

Once a year, the Sponsor shall provide a list of all suspected serious adverse reactions which have occurred during the period in question (Annual Safety Report) to regulatory authorities as applicable or required.

21.7 PROCEDURES FOR REPORTING ADVERSE EVENTS

Adverse events occurring after the subject has signed informed consent will be reported in the source documents and recorded on the appropriate AE eCRF pages.

It is not necessary to complete an AE eCRF page for chronic medical conditions present at enrollment that remain stable during the trial. However, if a medical condition present at enrollment worsens in intensity or frequency, it should be reported as an AE. It is not necessary to complete an AE eCRF for fluctuations in the disease under study if: these fluctuations are adequately captured by the efficacy assessments, and the degree of variation in frequency or severity is typical of the disease under study. An AE eCRF must be completed if the disease course is atypical or there is development of new signs or symptoms related to the disease under study.

Investigators should observe the following guidelines when recording AEs on the AE eCRF pages: use recognized medical terms; do not use jargon, colloquialisms or abbreviations; record a diagnosis (i.e., disease or syndrome) rather than component signs and symptoms (e.g., migraine rather than headache, nausea, transient visual loss); if a diagnosis is not feasible, record component signs and symptoms; AEs occurring secondary to other events (e.g., sequelae) should be identified by the primary cause.

21.8 PROCEDURES FOR REPORTING SERIOUS ADVERSE EVENTS

SAEs and other specified special reporting situations require expedited reporting to the Sponsor regardless of relationship to study drug. **The Investigator must report all SAEs to sponsor by phone AND by email as soon as possible but within no longer than 24 hours of observing or learning of the event.** The initial SAE report should include all case details that can be gathered within 24 hours of the event. Additional SAE pages may be submitted later as the case evolves or additional information becomes available.

The SAE should be reported immediately to Sponsor at:

[contact]

Or

[contact]

The completed SAE Report should be emailed immediately to the sponsor at:

Email: [name]

Additional relevant information or clinical follow-up should be emailed to the same contact as soon as it becomes available.

21.9 FOLLOW-UP FOR ADVERSE EVENTS AND SERIOUS ADVERSE EVENTS

All AEs will be followed until resolution or until the subject's participation in the study ends. However, SAEs and non-serious AEs assessed by the PI and the medical monitor as related to AMG 714 will be followed until resolution or until the PI and the medical monitor assess them as "chronic" or "stable," even if this requires extending follow-up beyond the usual duration of study participation. The Sponsor should be contacted regarding subjects who require follow up beyond the usual study duration.

AE and SAE care and follow-up will be similar for subjects traveling to the study site from countries other than the study site country.

21.10 SAFETY REVIEW COMMITTEE

Safety will be monitored throughout the study by the Sponsor and by a panel of independent experts, the DSMB. The DSMB is enabled and is expected to review any or all available study data on an ongoing basis in an unblinded fashion, as deemed appropriate for protection of subject safety. The DSMB will be formed before the start of study enrollment. The members of the DSMB will not be members of the AMG 714 study team, and will include at least one physician and one statistician.

If any of the stopping rules are met, an ad-hoc meeting of the DSMB will occur to assess the adverse events or findings. Safety findings will be reported to the investigators, the IRBs/IECs, and any other appropriate regulatory authorities.

After determination of the cause and significance of safety events, the DSMB is empowered to recommend continuing enrollment, pausing of enrollment, ceasing dosing, changing the protocol and study assessments to enhance subject safety, or terminating the study, as appropriate. If the investigation indicates with a high probability that the observed safety event was due to an identifiable cause other than the study drug, the DSMB may recommend continuation of study enrollment.

A separate DSMB Charter, finalized prior to the first DSMB meeting, outlines the specific guidelines for all DSMB activities. DSMB decisions will be communicated to the Investigators by the clinical study team.

22 DATA ANALYSIS AND STATISTICS

In addition to this section of the study protocol, a statistical analysis plan (SAP) and a PK analysis plan will be developed and finalized prior to the final database lock and unblinded data analysis. The SAP will provide a detailed description for the handling of missing data, subject eligibility criteria for the analysis, and statistical methodology for the data summary and between-group comparisons.

In addition to the main analyses, pre-specified subgroup analyses may include:

- Previous treatment for RCD-II
- Dietary transgressions (gluten consumption) based on serial iVYLISA GIP testing and on the dietitian's assessment
- Sex
- Duration of disease
- Age of onset
- Site

Non-evaluable subjects will include subjects missing one of the two biopsies and subjects dropping out of the study before Week 6. If a discontinuation occurs on or after Week 6 the subject is considered evaluable. The non-evaluable subjects will be excluded from the PP population.

The primary analyses will be based on the PP population. The PP population is defined in Section 22.2.

22.1 SAMPLE SIZE DETERMINATION

The CELIM-RCD-002 study is an exploratory proof-of-concept (POC) study of an experimental medication, AMG 714, in RCD-II patients. While it will be the first such study sponsored by a pharmaceutical company, the straightforward design is based on several academic studies (Goerres *et al.*, 2003; Brar *et al.*, 2007; Tack *et al.*, 2011a, 2011b) as well as on the nonclinical proof-of-principle signal obtained with AMG 714 in intestinal explants from patients with RCD-II (Malamut *et al.*, 2010).

The sample size is based on the size of previous academic studies. Published prospective academic studies have ranged from 13 to 18 patients total (Tack *et al.*, 2011a, 2011b) and CELIM-RCD-002 will be the largest prospective trial ever conducted in RCD-II, a very rare malignant disease.

The sample size of approximately 24 subjects (16 subjects in AMG 714 arm and 8 subjects in placebo arm) has been calculated to achieve at least ~ 80% power to detect a 20 percentage point difference in the primary endpoint, the difference in the baseline-to-Week 12 reduction of % aberrant IELs vs total IELs between the AMG 714 arm and placebo arm.

This sample size calculation was based on the following assumptions:

- Two-sided type one error rate $\alpha = 0.1$
- Power $1-\beta = 0.8$
- Analysis method: one-way ANOVA by SAS® (proc power)
- 2:1 allocation ratio between the AMG 714 and placebo arms
- Common SD = 17.4 for the baseline to Week 12 reduction in % aberrant IELs as assessed by low-cytometry
- Mean change of 20 percentage points and 0 percentage points in the baseline to Week 12 reduction in % aberrant IELs in the AMG 714 and placebo arms, respectively
- No drop-outs accounted (efforts will be made to replace drop-outs before Week 6 and/or subjects who do not provide the second biopsy)

The standard deviation used for the sample size calculation is computed from the % aberrant IEL (obtained by flow cytometry) data from 13 subjects treated with cladribine (subset of the patients reported in Tack *et al.*, 2011).

22.2 POPULATIONS FOR ANALYSIS

The populations for analysis will be intention to treat (ITT, safety population who at least received one dose of investigational product) and the per protocol population (PP, efficacy, i.e., available and evaluable pre- and post-biopsy information).

PP Population: The PP population will exclude non-evaluable subjects and subjects with major protocol deviations thought to impact the ability to assess the effect of treatment. Exclusion of subjects from the PP set will be reviewed, documented and approved before the study is unblinded to the study Sponsor. The criteria for excluding subjects from the PP population will be specified in the SAP.

ITT (Safety) Population: This population consists of all randomized subjects who have received at least one dose of the study drug. Subjects will be analyzed in the treatment group they were randomized to. Subjects with only one measurement available will be excluded from the ITT population for all endpoints defined as change from baseline. The safety population is by definition the same as the ITT population.

Main efficacy measures which require pre- and post-treatment biopsies will be based on the PP population (at least 2 biopsies, the second at least on Week 6 or later). Continuous variables will be analyzed based on the ITT population. Demographics and safety parameters will be analyzed using the ITT population.

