22.8.2 Other Safety Assessments

The following safety parameters will be assessed:

- Clinical laboratory tests
- Physical examination
- Vital signs

All safety variables will be summarized by treatment group. Some of these variables will be tabulated by treatment and by visit.

For the assessment of immunogenicity, the number and percent of subjects who developed binding antibodies and who developed neutralizing antibodies will be determined.

In addition to the abovementioned safety assessments, all females will have urine or serum pregnancy tests throughout the study.

All safety variables will be tabulated by treatment group and time point (if feasible) using the ITT population.

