ITT (safety) population: this population consists of all randomized subjects who have received at least one dose of the study drug. The safety population is by definition the same as the ITT population. If a subject had a misallocated treatment on a specific visit, observed upon unblinding, a secondary sensitivity analysis will be performed on as treated basis.

Main efficacy measures which require pre- and post-treatment biopsies will be analysed using the PP population (at least 2 biopsies, the second on Week 6 or later). Continuous efficacy variables will be analysed based on the ITT population. Demographic and baseline variables will be assessed using both ITT and PP populations. Safety parameters will be analysed using the ITT population. Compliance data will be reviewed to assure subjects were treated as randomized.

A detailed description of the study populations and subjects included will be given in the Subject Classification Document, which will be finalized before the database lock.

Table 1 Data sets to be used in the analysis

Primary variable ²	Secondary variables ^{1,2}	Exploratory/PD variables ¹	Safety variables	Demographic and baseline variables
PP	ITT PP	ITT PP	ITT	ITT PP

¹PP set used for biopsy-dependant variables and ITT for all other variables.

²PP population will exclude atypical RCD-II patients (patients with a different phenotype of the aberrant IELs) for the purpose of analysis of Immunological Response 1 and 2.

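### The main safety tables follow the randomised arm, so findings after AMG 714 given in error to a placebo subject would be counted under placebo

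*Protocol*

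**What the plan says.** Protocol 22.2 defines a single ITT (Safety) population of randomised subjects who were dosed. It gives the grouping rule, "Subjects will be analyzed in the treatment group they were randomized to", and adds: "The safety population is by definition the same as the ITT population". Protocol 22.8.2 puts the tables on that set: "All safety variables will be tabulated by treatment group and time point (if feasible) using the ITT population".

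SAP 8.1 repeats that the two populations are the same and says: "Safety parameters will be analysed using the ITT population". It does not restate the randomised-arm sentence, but it does not replace it for the main tables either. Its one departure is: "If a subject had a misallocated treatment on a specific visit, observed upon unblinding, a secondary sensitivity analysis will be performed on as treated basis". It also says: "Compliance data will be reviewed to assure subjects were treated as randomized". That is a check and does not reassign anyone.

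SAP 8.8.1 (adverse events), 8.8.2 (laboratory tests) and 8.8.5 (immunogenicity) all tabulate by treatment group.

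**The concern.** Analysis by randomised arm protects an efficacy comparison, but it is a poor default for safety. A reader of an adverse event table wants to know what happened to people exposed to the drug. If a placebo-randomised subject is given AMG 714, counting later findings under placebo raises the placebo rate and leaves those findings out of the AMG 714 rate. Both errors make the drug look safer.

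Safety and tolerability is the trial's secondary objective, and immunogenicity is a listed safety endpoint. Protocol 2.2 reports only one antibody-positive subject among about 200 dosed, so a single drug-induced antibody shown under placebo could mislead. The SAP itself foresees misallocation at a visit. It does not say how to classify a subject who received both products over seven infusions, so that choice would be made after the treatment codes are known.

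**Working it through.** **Which rule governs the main tables.** Protocol 22.2 groups the safety population by randomised arm. SAP 8.1 keeps safety on ITT and labels the alternative as "a secondary sensitivity analysis will be performed on as treated basis". An as-treated analysis is a sensitivity analysis only if the main one is not as treated, so the two documents agree that the main safety tables are as randomised. SAP 8.9 names dosing deviations among its additional analyses, but allows those to be confined to biopsy-dependent efficacy endpoints, so it does not fill the gap for safety.

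**Arm sizes.** Protocol 22.1 plans 16 AMG 714 and 8 placebo subjects. That figure reproduces. With a difference of 20, SD 17.4 and two-sided alpha 0.10, the noncentrality is 20 / (17.4 × √(1/16 + 1/8)) = 20 / 7.53 = 2.65 on 22 degrees of freedom. Power is 82.3%, against 77.3% at 14:7. Nothing below changes it.

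**Effect of a misallocation.** The documents give no misallocation rate, so the counts here are assumptions. Let k placebo-randomised subjects receive AMG 714 and then have the event. Let m AMG 714-randomised subjects have it, and no other placebo subject.

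- As randomised, AMG 714 minus placebo = m/16 − k/8.
- By treatment received, AMG 714 minus placebo = (m + k)/(16 + k) − 0/(8 − k).

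| k, m | As randomised (AMG 714 vs placebo) | Difference | By treatment received (AMG 714 vs placebo) | Difference |
|---|---|---|---|---|
| 1, 0 | 0/16 vs 1/8 (0% vs 12.5%) | −12.5 | 1/17 vs 0/7 (5.9% vs 0%) | +5.9 |
| 1, 2 | 2/16 vs 1/8 (12.5% vs 12.5%) | 0 | 3/17 vs 0/7 (17.6% vs 0%) | +17.6 |
| 2, 2 | 2/16 vs 2/8 (12.5% vs 25.0%) | −12.5 | 4/18 vs 0/6 (22.2% vs 0%) | +22.2 |

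Each such subject adds 1/8 = 12.5 points to the as-randomised placebo rate. In the first row the two displays differ by 5.9 + 12.5 = 18.4 points and have opposite signs.

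**Mixed exposure.** The table moves the whole subject. If the wrong infusion came after one or more correct placebo infusions, the subject was also at risk on placebo and belongs in that denominator for the earlier period. With k = 1 and m = 0 the comparison is then 1/17 vs 0/8, and the difference is still +5.9 points.

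**Persistence.** Protocol 1.6 gives a half-life of 3 weeks. From a Week 10 dose to Week 16 is 6 weeks, or two half-lives, so 0.5² = 25% would remain. Protocol 18.3 expects protein-losing enteropathy in this disease, which could shorten that.

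**The case against.** The strongest reply is that the case is already provided for and could hardly go unnoticed.

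- The as-treated sentence in SAP 8.1 closes the paragraph that defines the ITT (safety) population, so it most naturally covers safety. A reader might infer that no as-treated safety output is planned. The text does not support that.
- Safety is descriptive in about 24 subjects, with subject-level output. SAP 8.5 tabulates exposure by visit and lists doses. SAP 8.8.1 lists all adverse events and requires narratives for SAEs and for events leading to discontinuation. Laboratory and antibody results are listed. The DSMB sees unblinded safety data throughout. A claim that harm would be hidden goes too far.
- Controls lower the likelihood. An unblinded preparer works from an electronic assignment, with vials that are labelled by product and differ in colour.
- The 18.4-point contrast is a constructed single-event case. Fisher's exact two-sided p is 8/24 = 0.33 as randomised and 1.0 by treatment received, so neither display would support a safety conclusion.
- The reverse error, an AMG 714 subject given placebo at one visit, leaves the subject under AMG 714 under either rule, apart from any time before a first AMG 714 dose.
- Counting any exposed subject wholly under AMG 714 would bring its own bias, because events before exposure would be charged to the drug.

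Most of this stands, and it limits the size of the point. The last item is why attribution should start at the first AMG 714 dose. What remains is that the main tables, which are the ones usually summarised and quoted, follow the less suitable rule, and that no convention exists for a subject who received both products.

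**Conclusion.** The point holds as a conditional weakness in how the main safety tables are defined. If a placebo-randomised subject receives AMG 714, later adverse events, laboratory changes and antibodies are counted under placebo in those tables, at 12.5 points on the placebo rate per affected subject with the event. This assumes that the planned 16 and 8 are dosed and that a misallocation occurs in that direction.

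A reader might infer from the misallocation clause, which the SAP's document history lists among the additions in version 2.0, that an error had already happened. The documents report none and give no rate. Nor do they support a claim that the trial's safety comparison is in fact distorted by 18 points: that contrast rests on one assumed subject with the only event of its type. Sample size, power and alpha are unaffected. The change is worth making because treatment received is the less biased and standard basis for safety, and it is cheap.

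**What to change.** Keep ITT by randomised arm for efficacy. In protocol 22.2 and SAP 8.1, define the main safety set by treatment received, and fix the rule before unblinding:

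- A subject with at least one AMG 714 dose counts under AMG 714 for events and assessments from the first AMG 714 dose onward.
- Findings on treatment before that dose are attributed to placebo.
- The rule applies to the adverse event, laboratory, vital sign and anti-drug antibody tables, with a stated convention for denominators when a subject has time under both products.
- Misallocated doses are listed by visit.
- The as-randomised safety tables may be kept as the sensitivity analysis.

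The cost is one derived actual-treatment variable, the mixed-exposure convention and short edits to both documents. The inputs already exist: protocol 18.7.5 requires dispensing records by subject, batch, date and quantity, and SAP 8.5 already tabulates exposure by visit. If no misallocation occurs, no table changes.
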